The PI will review all AE assessments and will follow up to obtain any further information necessary prior to approving the report. PI approval of the AE report will be indicated with her signature and date.

Severity will be assessed using the following guidelines:

- Mild-The adverse event may or may not be noticeable to the participant and does not significantly impact the participant's ability to complete activities of daily living (ADL's).
- Moderate- The adverse event is noticeable and causes some inconvenience and impact on the ability to complete ADL's.
- Severe-The adverse event has a very significant impact on the participant's ability to complete ADL's.

Causality, or relatedness to study intervention or procedures, will be categorized as:

- Definitely Related: The adverse event is clearly related to the study intervention / procedure – i.e., an event that follows a reasonable temporal sequence from administration of the study intervention, follows a known or expected response pattern to the suspected intervention, that is confirmed by improvement on stopping and reappearance of the event on repeated exposure and that could not be reasonably explained by the known characteristics of the subject's clinical state.
- Probably Related: The adverse event is more likely than not attributable to study intervention or procedures. i.e While other causes of the event may be possible, the temporal relationship of the event to the study intervention or procedure and other factors lead to the conclusion that the most likely cause is the study intervention/procedure.
- Possibly Related: An adverse event that follows a reasonable temporal sequence from administration of the study intervention and follows a known or expected response pattern to the suspected intervention, but that could readily have been produced by a number of other factors.
- Not Related: The adverse event is clearly not related to the study intervention /procedure - i.e., another cause of the event is most plausible; and/or a clinically plausible temporal sequence is inconsistent with the onset of the event and the study intervention and/or a causal relationship is considered biologically implausible.

Expectedness refers to the whether the AE is anticipated based on current knowledge of the nature, severity, and frequency of the risks of the study intervention, as defined in the protocol and in the informed consent form. Thus, an event may be listed as a known potential risk, but if the event occurs in a more severe intensity or occurs more frequently than what is known, the event would be considered unexpected.

Adverse Event Reporting

The PI will ensure that all AE's that meet reportability criteria will be reported to the IRB within the expedited IRB-specified timeframe. The KU IRB requires reporting of AE's (whether serious or non-serious) that are determined to be related or probably related to study participation and that were unexpected. The timeframe for reporting AE's/ SAE's that meet these criteria is within five working days of the PI learning of the event. An exception to this timeframe is the reporting of deaths that are determined to be related or probably related to study participation. These must be reported within 24 hours by phone or email, with a full adverse event report submitted within five working days.

Any SAE that is related or probably related to study participation and that is unexpected will also be reported expeditiously to the NIA program officer and to the independent safety officer, within 48 hours of knowledge of the SAE. However, SAE's that result in death that are determined to be related to the study will be reported to the NIA program officer within 24 hours of learning of the event.

A summary of all AE's/ SAE's will be reported to the NIA program officer on a quarterly basis. The PI and medical monitor will also review all AE's/ SAE's on quarterly basis as described below in the Data and Safety Monitoring Plan.

Data and Safety Monitoring Plan

The data and safety monitoring plan consists of oversight by an independent safety monitor.

At the conclusion of each cohort of the study intervention, the study team will provide a report to the independent safety monitor detailing all AE's that have occurred to date. Following the review of safety data, the safety monitor will document his assessment of safety and his determination to: 1) continue the study without any modifications, 2) continue the study, but

only with additional monitoring or other specified modifications to the protocol or 3) discontinue the study due to safety issues.

III. Subject Participation

A. Recruitment: The PI and the Outreach and Recruitment Core at the KU ADRC will contact potential participants through the Clinical Cohort registry via recruitment letter, email, and phone. Secondly, [name] and support personnel will recruit through the delivery of Aging With Grace educational curriculum to faith-based and AA serving organizations and will distribute flyers during each presentation. Lastly, [name] community partners (Bright Business Solutions, BHCC, and Heal Black Men) and consultants will each help recruit AAs through their personal connections and resources. BHCC, Bright Business Solutions, Health Black Men, and consultants will be provided with flyers about the study to provide to their personal connections. Community members who are interested in participating in the study will reach out to the PI or support personnel via email or phone.

B. Screening Interview/questionnaire: The PI or support personnel will provide details regarding the nature of the study, and will conduct an interview to screen for eligibility for the study, following verbal consent from the participant to proceed with the screening questions. This interview will include a review of medical conditions, the completion of the AD8 measure to screen for cognitive impairment, the completion of the PHQ9 measure to screen for active depression, and a review of all eligibility criteria that can be completed prior to baseline to determine eligibility. One eligibility criterion that cannot be completed prior to baseline is Exclusion (f): Uncontrolled hypertension, by history, or as indicated by sittingsystolic blood pressure >165 mmHg or diastolic blood pressure >95 mmHg at the baseline visit. If an initial blood pressure reading is higher than this, an additional attempt (at this visit or on another day) could be used before excluding a patient for uncontrolled hypertension. Individuals deemed eligible via the phone screen will be placed into 1 of 3 cohorts, provided the participant does not meet exclusion criterion (f) at the baseline visit.

C. Alternatives to Participation: none

D. Costs to Subjects: There is no cost to subjects for participation in this study.

E. How new information will be conveyed to the study subject and how it will be documented: No information regarding cardiometabolic health, nutritional status, or cognition will be conveyed to the participant.

F. Payment, including a prorated plan for payment: Each participant will receive groceries worth up to \$50 per week (average total of \$600) that will be provided weekly for 12 weeks. Groceries will be limited to foods within the 10 distinct food groups of the MIND+SOUL diet. These foods will be selected each week from a community supermarket and ordered by the research team. Focus group participants will receive a \$25 Visa gift card for their participation.

G. Payment for a research-related injury: The likelihood for research-related injury is extremely low and there will be no payment to the study participant for such injury. We will include the following text in the consent form: "If you have a physical injury as a result of participating in this study, treatment will be provided for you at the usual charge. Treatment

may include first aid, emergency care and follow-up care, as needed. Claims will be submitted to your health insurance policy, your government program, or other third party. You will be billed for the costs that are not covered by the insurance. You do not give up any legal rights by signing this form."

IV. Data Collection and Protection

- A. Data Management and Security:** Information from these tests will be entered into a research database. The PI and SC will supervise the data acquisition. Data will be coded for confidentiality and only the PI, study team, and statistician will have access to the code. Hard copies of study files are kept in a dedicated, locked cabinet in a badge-access area. Subject data will be coded prior to sending it to the statistician for statistical analyses.
- B. Sample / Specimen Collection:** N/A
- C. Tissue Banking Considerations:** N/A
- D. Procedures to protect subject confidentiality:** Much of the study data will be direct entered (entered as it is collected and not first recorded on paper forms) onto custom developed electronic source document forms created in Research Electronic Data Capture (REDCap). Exceptions to this direct entry method include the cognitive testing scores, which will be retrieved from the NIH Toolkit portal. Other measures may be recorded on paper forms in the event access to the REDCap database is disrupted for any reason.

REDCap is a secure, web-based application designed to support data capture for research studies, providing: 1) an intuitive interface for validated data entry; 2) audit trails for tracking data manipulation and export procedures; 3) automated export procedures for seamless data downloads to common statistical packages; and 4) procedures for importing data from external sources. REDCap on the KUMC campus sits on a HIPAA compliant, password protected server. The KU ADRC has extensive experience building and maintaining REDCap databases, including those used for the preliminary data in this application. Confidentiality is strictly safeguarded by HIPAA-compliant standards.

- E. Quality Assurance / Monitoring:** The study team will perform source data verification and self-assessment of records at the completion of each cohort of the intervention to ensure that data are accurate.

V. Data Analysis and Reporting

- A. Statistical and Data Analysis:** Information from these tests will be entered into a research database. The PI, SC, and study team will supervise the data acquisition. Data will be coded for confidentiality and only the PI, SC, study team and statistician will have access to the code. Hard copies of study files are kept in a dedicated, locked cabinet in a badge-access area. Subject data will be coded prior to sending it to the statistician for statistical analyses.

Using an ANOVA model, 10 samples per time point (total 3 time points) will achieve 80% of power to detect a maximum change of the standardized measurement (raw measurement divided by its standard deviation) across the 3 time points with a magnitude 1.3 (A

magnitude <1 will mean the change is less than the noise level. I would consider a magnitude of 1.3 a subtle or a medium sized change.).

Focus group data will be analyzed using the constant comparative coding analysis.²⁷ Specifically, we will assess if the emerged themes were consistent across the two groups. The analysis will occur in three stages.²⁸ During the first stage of open coding, data will be placed into small units and will be coded for each unit. Axial coding will occur during the second stage in which the codes will be grouped into categories. Selective coding will occur during the third stage in which the PI will construct themes that express the content of each of the identified grouped categories.

B. Outcome: We expect to determine feasibility and acceptability of the MIND+SOUL diet. Feasibility will be assessed by 1) collecting measures including body composition (DXA), cardiometabolic risk factor assessments (blood pressure and blood draw), dietary assessments (NHANES dietary screener questionnaire and skin carotenoid assessment), and cognitive assessments (NIH toolbox), 2) recruitment throughout the intervention including reasons for refusal to participate and 3) retention rates including attrition (80% compliant) rate of completion of the intervention (i.e. number/percentage of participants who complete all aspects of the intervention including cooking classes and coach directed dietary call support). Acceptability will be assessed post-intervention using two REDCap online surveys, (see attachments) that will capture the overall experience and perception of the MIND+SOUL diet. For the first survey, acceptability will be evaluated on the theoretical framework of acceptability and evaluate the following constructs: affective attitude (how an participant feels about the MIND+SOUL intervention), burden (perceived amount of effort required to participate in the MIND+SOUL intervention), ethicality (extent to which the intervention has good fit with the participants value system), perceived effectiveness (extent to which the intervention is perceived as likely to achieve its purpose), and self-efficacy(participants confidence that they can perform the behaviors required to participate in the intervention). The second survey will evaluate satisfaction with the MIND+SOUL diet using a visual analog scale.

C. Study results to participants: A letter will be mailed to study participants at the end of the study to provide information on the general results of the study.

D. Publication Plan: Publication of the results of this study will be governed by the policies and procedures developed by the study team.

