To address Aim 1, we will conduct a purposive sampling and recruit participants (n=30) through the KU Alzheimer's Disease Research Center (KU ADRC) AA Clinical Cohort and the community and screen for study eligibility. Additionally, participants will be recruited from flyers and announcements at distributed by community partners (Black Health Care Coalition and New Bethel Church Community Development Corporation). Inclusion criteria for eligible participants include 1) self-identifying as AA or Black, 2) aged 55 years and older, 3) English speaking, 4) cognitively normal with an Eight-item Interview to Differentiate Aging and Dementia (AD8) < 2, 5) 1 or more cardiovascular risk factors 6) females of child-bearing potential (i.e., pre-menopausal) must have a negative urine pregnancy test at the screening visit and must agree to use of contraception throughout the trial. The approved methods of contraception are abstinence, the consistent use of an approved oral contraceptive (birth control pill or "the pill"), an intrauterine device (IUD), hormonal implants, contraceptive injection, double barrier method (diaphragm with spermicidal gel or condom with contraceptive foam). Using a small single arm

trial we will test the community-informed culturally tailored diet and education plan that was developed in a previous study (IRB #00146894) with a primary goal of evaluating feasibility and acceptability of the diet and its implementation.

Aim 2: Explore cognitive functions associated with the brain-healthy soul food diet intervention as preliminary data to design a RCT.

To address aim 2, we will assess change in cognition among AA in a single arm trial. Participants will be scheduled to complete a cognitive measurement session (approximately 30 minutes) at the KU ADRC at the baseline and 12 week mark. The NIH Toolbox will be used to assess cognition using one test in each of the following domains: memory, language, reading, vocabulary, processing speed, and executive function.² Specifically the following tests will be administered: NIH-TB List Sorting Working Memory Test, NIH-TB Picture Vocabulary Test, NIH-TB Oral Reading Recognition Test, and the NIH-TB Pattern Comparison Processing Speed Test, and NIH-TB Flanker Inhibitory Control and Attention. Between group differences will be analyzed using ANOVA.

Primary Outcome

Feasibility and Acceptability Data Collection:

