Feasibility will be assessed by 1) collecting measures including cardiometabolic risk (e.g. blood pressure and blood draw – lipid profile, inflammation), body composition (DXA), dietary assessments (NHANES diet screening questionnaire and skin carotenoid assessment), and cognitive assessments (NIH toolbox), 2) recruitment throughout the intervention including reasons for refusal to participate and 3) retention rates including attrition (80% compliant) rate of completion of the intervention (i.e. number/percentage of participants who complete all aspects of the intervention including cooking classes and coach directed dietary call support).

Acceptability will be assessed post-intervention using two REDCap online surveys,³ that will capture the overall experience and perception of the MIND+SOUL diet. For the first survey acceptability will be evaluated on the theoretical framework of acceptability and evaluate the following constructs⁴: affective attitude (how an participant feels about the MIND+SOUL intervention), burden (perceived amount of effort required to participate in the MIND+SOUL intervention), ethicality (extent to which the intervention has good fit with the participants value system), perceived effectiveness (extent to which the intervention is perceived as likely to achieve its purpose), and self-efficacy(participants confidence that they can perform the behaviors required to participate in the intervention). The second survey will evaluate satisfaction with the MIND+SOUL diet using a visual analog scale.

Secondary Outcomes

Data from our secondary outcomes will form the basis of estimating power and sample size for a future randomized controlled clinical trial.

Baseline descriptive statistics including demographic, psychosocial, dietary and behavioral characteristics will be measured.

Cardiometabolic risk: Cardiometabolic risk will be measured by 2 items; blood pressure and blood draw. Blood pressure will be measured using the Omron 5 series blood pressure monitor.⁷ Blood draw will be administered to collect measurements of lipid profile, glucose metabolism, inflammation, APOE-

$\epsilon 4$ genotyping, and other AD related fluid cardiometabolic biomarkers. All cardiometabolic risk assessments will be collected at baseline and at the 12-week mark.

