Aim 1: Assess feasibility and acceptability of the adapted brain-healthy diet intervention in a single arm pilot trial. A purposive sample (n=30) aged 55 years and older who self-identify as African American or Black will participate in a single arm dietary intervention trial to evaluate feasibility and acceptability of the diet and its implementation.

Aim 2: Explore cognitive functions associated with the brain-healthy soul food diet intervention as preliminary data to design a RCT. We assess change in cognition among AA in a single arm trial.

B. Study Type and Design:

This is a single arm trial designed to pilot test an adapted brain healthy diet intervention among older AA (n=30). Specifically, this study aims to evaluate the feasibility and acceptability of the brain healthy soul food diet intervention. As secondary outcomes, this study aims to assess body composition, cardiometabolic risk, nutritional health status, and changes in cognition among older AA to form the basis of estimating power and sample size for a future full-scale randomized controlled clinical trials.

Study visit summary

In Year 1, we will conduct purposive sampling and recruit participants (n=30) through the KU ADRC AA Clinical Cohort and KU ADRC recruitment database, through partnership with our community partners [name] (CEO of Bright Business Solutions), [name] (Executive Director of Black Health Care Coalition), [name] (CEO of Black Men HEAL) and through the delivery of Aging With Grace; a culturally tailored dementia prevention curriculum within the community. Additionally, participants will be recruited from flyers distributed by consultants.

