Counseling: Counseling: Counseling will consist of one-on-one sessions with a health coach who will provide MIND+SOUL diet continued education and on-going support throughout the diet intervention. This support will consist of education and recommendations specific to the participant's needs, preferences, and local context. The health coach will help participant set dietary goals in relation to the MIND+SOUL diet, help participants develop an action plan for certain situations (i.e. holiday parties, vacations), and provide encouragement in regards to the formation of healthy eating habits. Zoom conference calls will occur bi-weekly for 12-weeks. Each Zoom conference (6 total per participant) is anticipated to last 15-20 minutes each time, with exception to the first Zoom conference call which is anticipated to up to 30 minutes.

Financial support: To improve adherence to the MIND+SOUL diet each participant will receive weekly groceries worth up to \$50 per week (total average of \$600) that will be provided to each participant for 12-weeks. Groceries will be limited to foods within the 10 distinct food groups of the MIND+SOUL diet. These foods will be selected from each week from a community supermarket.

C. Sample size, statistical methods, and power calculation

Single arm: Participants will be in a single arm trial using 3 cohorts (cohort 1 – 10 people, cohort 2 – 10 people, cohort 3 – 10 people). Rationale: Use of a single arm trial will allow for assessment of feasibility and acceptability of the MIND+SOUL diet. Additionally, use of 3 cohort will allow for an opportunity to make revisions between each cohort to further enhance feasibility and acceptability of the MIND+SOUL diet.

Individuals deemed eligible will be placed into 1 of 3 cohort.

Sample Size: A total of 30 participants will be enrolled in the pilot study. Cohort 1 will consist of 10 participants, cohort 2 will consist of 10 people, and cohort 3 will consist of 10 people.

D. Subject Criteria:**1. Inclusion Criteria**

- a. Identify as African American or Black
- b. Age 55 and older
- c. English Speaking
- d. 1 or more of the following CVD risk factors (high blood pressure, high cholesterol, controlled type 2 diabetes overweight/obesity with a BMI of 25 or more as calculated from weight and height at baseline visit)
- e. Cognitively Normal with an AD8 <2 (normal cognition)

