- f. Females of child-bearing potential (i.e., pre-menopausal) must have a negative urine pregnancy test at the screening visit and must agree to use of contraception throughout the trial. The approved methods of contraception are abstinence, the consistent use of an approved oral contraceptive (birth control pill or "the pill"), an intrauterine device (IUD), hormonal implants, contraceptive injection, double barrier method (diaphragm with spermicidal gel or condom with contraceptive foam).

2. Exclusion Criteria

- a. No CVD risk factors
- b. AD8 equal to or greater than 2
- c. Diagnosed with type 1 diabetes
- d. Uncontrolled diabetes type 1 or type 2
- e. Existing diet plan that subject is unable to pause during trial
- f. No internet connection
- g. Uncontrolled hypertension, by history, or as indicated by sitting systolic blood pressure >165 mmHg or diastolic blood pressure >95 mmHg at the baseline visit. If an initial blood pressure reading is higher than this, an additional attempt (at this visit or on another day) could be used before excluding a patient for uncontrolled hypertension
- h. Neurological diseases that impact cognition
- i. Other medical conditions likely to be negatively impacted by a diet change or that could confound the study data (i.e. Celiac Disease, Ulcerative Colitis)
- j. Unable or unwilling to provide written consent
- k. PI determination that study is unsafe or unsuitable for the participant
- l. Active depression as determined by a score of 5 or above on the PHQ9 and deemed to be clinically significant by the medical monitor

3. Withdraw/Termination criteria:

- a. There is no withdraw or termination criteria
- b. Participants are allowed to participate in other observational studies during their enrollment period, but not interventional trials

Total enrollment is anticipated to last between 3-4 months total, with 1-1.5 months of recruitment per cohort.

E. Specific methods and techniques used throughout the study

This study will require two study visits. Outcome data will be collected at baseline and at the 12 week mark (+/- 2 weeks). The total time commitment for visit 1 is 2.5 hours and visit 2 is 2.5 hours.

Visit 1 – Baseline Evaluation

Estimated duration: 2.5 hours

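### Aim 2 asks about within-person change in one arm, but its only stated analysis is an ANOVA of between-group differences, which does not answer that question

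*Combined protocol and SAP*

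**What the plan says.** Under Aim 2 in section I.A the protocol states that "we will assess change in cognition among AA in a single arm trial", with testing at baseline and week 12. The same paragraph ends with its only analysis sentence: "Between group differences will be analyzed using ANOVA". The groups are not defined.

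Section II.C describes the structure: "Participants will be in a single arm trial using 3 cohorts", each of 10 people, so that the intervention can be revised between cohorts. Section II.E sets two measurement occasions: "Outcome data will be collected at baseline and at the 12 week mark".

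Section V.A contains no analysis of cognition. It has one power statement, opening "Using an ANOVA model, 10 samples per time point (total 3 time points"), which claims 80% power for a maximum change of 1.3 SD. No section names a paired test, a change-score analysis, a mixed model or a repeated-measures ANOVA.

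On the use of the results, Secondary Outcomes in section I.A says: "Data from our secondary outcomes will form the basis of estimating power and sample size for a future randomized controlled clinical trial".

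**The concern.** The quantity of interest is the average 12-week change in the same people. The stated analysis compares groups, and there is no comparison group. Two readings are possible.

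- **Groups are the cohorts.** The test asks whether the three cohorts differ from one another. It can be non-significant however large the overall change is.
- **Groups are the visits, treated as independent samples.** With complete data the mean difference is right. But each person's two scores are handled as unrelated, so with a positive pre-post correlation the standard error is too large and the confidence interval too wide.

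At stake is how well this pilot describes the change in cognition, and whether the plan commits to reporting what a future trial needs: the mean change with its interval, the SD of change and the pre-post correlation. The plan as written commits to none of these.

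**Working it through.** **Inputs from the protocol.** N = 30 in three cohorts of 10 (II.C); two visits (II.E); 10 samples at each of three time points, 80% power and a maximum change of 1.3 in units of the raw SD (V.A).

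**Assumptions, because the documents give no values.** Two-sided alpha 0.05; unit SD at each visit; complete data; pre-post correlation ρ of 0.5, 0.7 or 0.8; an illustrative change of 0.5 SD.

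**1. The plan's 80%.** For an independent one-way ANOVA, λ = n Σ(μᵢ − μ̄)²/σ², with 2 and 27 df.

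- Evenly spaced means (−0.65, 0, 0.65): λ = 10 × 0.845 = 8.45, power 69.1%.
- One mean apart (0, 0, 1.3): λ = 10 × 1.127 = 11.27, power 81.8%.

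For a repeated-measures ANOVA on 10 people with compound symmetry, λ is divided by (1 − ρ), with 2 and 18 df.

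| ρ | Evenly spaced | One mean apart |
|---|---|---|
| 0 | 66.4% | 79.4% |
| 0.3 | 82.2% | 91.9% |
| 0.5 | 93.2% | 98.0% |
| 0.7 | 99.5% | 99.9% |

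So 80% is close to the independent-samples calculation with one mean apart. Repeated measures reaches 80% only at ρ of about 0.26 (evenly spaced) or 0.01 (one apart). This suggests the independent version but does not prove it, since V.A states neither the mean pattern, alpha nor ρ. On either model, three time points of 10 do not match two visits and 30 people.

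**2. Groups as cohorts.** If all cohorts share one change, the noncentrality of an ANOVA on change scores is 0. In 20,000 simulated trials per setting, with common changes of 0, 0.5 and 1.3 SD and ρ of 0.5, 0.7 and 0.8, it rejected 4.6% to 5.2% of the time throughout.

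**3. Groups as visits.** The standard error used is √(2/N) = √(2/30) = 0.258 unpaired, and √(2(1−ρ)/N) paired. Their ratio is 1/√(1−ρ). Paired power uses the noncentral t with 29 df and noncentrality 0.5/SE, that is 2.74, 3.54 and 4.33. Unpaired power, type I error and detectable change were simulated on correlated data.

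| | ρ = 0.5 | ρ = 0.7 | ρ = 0.8 |
|---|---|---|---|
| Paired SE | 0.183 | 0.141 | 0.115 |
| Unpaired SE / paired SE | 1.41 | 1.83 | 2.24 |
| Mean 95% CI half-width, unpaired | 0.51 | 0.51 | 0.51 |
| Mean 95% CI half-width, paired | 0.37 | 0.29 | 0.23 |
| Power for 0.5 SD, unpaired | 47% | 47% | 46% |
| Power for 0.5 SD, paired | 75% | 93% | 99% |
| Change detectable with 80% power, unpaired | 0.67 | 0.64 | 0.62 |
| Change detectable with 80% power, paired | 0.53 | 0.41 | 0.33 |
| Type I error, unpaired (nominal 5%) | 0.7% | 0.08% | 0.01% or less |

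The textbook two-sample formula gives 0.74 SD as the unpaired detectable change. That assumes truly independent scores; the simulated values apply the unpaired test to correlated scores and are kinder to the plan.

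**4. The plan's own effect size.** At 1.3 SD both tests have about 100% power with 30 people.

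**The case against.** The strongest reply is that the sentence may be loosely worded rather than wrong. Section V.A speaks of an ANOVA for change over time points, and a repeated-measures ANOVA with two visits is the same as a paired t-test. The protocol does not say that an unpaired analysis will be run, and the 80% figure cannot settle the matter. That stands: the harm under the second reading depends on the independent-groups version being used. But the sentence specifies between-group differences, and nothing elsewhere corrects it.

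The size of the loss also rests on assumed values. At ρ = 0.3 the standard-error ratio is only 1.20 and paired power for 0.5 SD is 61% against about 47% unpaired; at ρ = 0 pairing gains nothing (47% against 48%). The 0.5 SD change is not in the protocol. All of this stands, and the figures should be read as a range. The cohort reading fails whatever ρ is.

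Finally, Aim 2 is exploratory, and the SD and correlation needed to size a randomized trial can be computed from the two-visit data whichever test is run. That also stands and limits the weight of the point. It does not make the stated analysis answer the stated aim.

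**Conclusion.** The concern holds. The stated analysis does not match Aim 2. Read as a comparison of cohorts, it carries no information about a shared change. Read as an independent comparison of visits, it overstates the standard error by 1.41 to 2.24 times at ρ of 0.5 to 0.8, and cuts power for a 0.5 SD change from 75–99% to about 47%. These figures assume 30 complete pairs, two-sided alpha 0.05 and a positive correlation that the documents do not give. The loss shrinks as ρ falls and is immaterial at a 1.3 SD change.

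The error is conservative, so it does not create false positives. The primary feasibility and acceptability outcomes are unaffected, and the data will support a correct analysis. It should be fixed before analysis, but it does not threaten the trial.

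**What to change.** Replace the Aim 2 analysis sentence with text to this effect:

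> For each continuous outcome, the mean baseline-to-week-12 change will be estimated with a 95% CI from a paired analysis (paired t-test, or a linear mixed model with time as a fixed effect and a participant random intercept). The SD of change and the pre-post correlation will be reported for planning the randomized trial. Change by cohort will be reported descriptively; if a time-by-cohort term is fitted, the main estimate is the change averaged over cohorts.

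In section V.A, replace the ANOVA power statement with one for two visits and 30 participants, for example:

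> A paired t-test on 30 complete pairs has 80% power for a change of 0.53, 0.41 or 0.33 SD at assumed pre-post correlations of 0.5, 0.7 or 0.8.

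It would be prudent to add an attrition case. If 80% of participants gave both measurements (0.8 × 30 = 24 pairs), the detectable changes would be 0.60, 0.46 and 0.38 SD. The protocol's 80% refers to completing the intervention, so its use here is an assumption.

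The cost is protocol wording only; no data or visits are added. The averaging clause matters. Under reference coding, the time coefficient in a time-by-cohort model is one cohort's change, with a standard error √3 = 1.73 times larger and power for 0.5 SD of 33%, 50% and 67% at ρ of 0.5, 0.7 and 0.8. Averaged over cohorts, power stays at 75%, 93% and 99%. Estimates for single cohorts of 10 will be imprecise in any case.
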